5 CRITERIA FOR EVALUATION

5.1 Primary Efficacy Endpoint

We will evaluate if there are genes which are statistically significantly upregulated or downregulated in specific cell populations, based on RNA sequencing.

For assessment of psoriasis improvement, we will use the Psoriasis Area and Severity Index (PASI) scoring system.

5.2 Secondary Efficacy Endpoints

- There are no secondary endpoints.

5.3 Safety Evaluations

- The biopsy site will be evaluated at time of suture removal for any signs of superficial infection.
- Patients will have standard follow-up visits to assess efficacy and side effects of tildrakizumab, as would any of our non-trial patients started on this medication.

6 SUBJECT SELECTION

6.1 Study Population

Subjects with a diagnosis of psoriasis or atypical psoriasis who meet the inclusion and exclusion criteria will be eligible for participation in this study.

6.2 Inclusion Criteria

1. Male or female ≥ 18 years of age at clinic visit.
2. Documentation of moderate-severe psoriasis or atypical psoriasis.
3. Written informed consent (and assent when applicable) obtained from subject or subject's legal representative and ability for subject to comply with the requirements of the study.

6.3 Exclusion Criteria

4. Presence of a condition or abnormality that in the opinion of the Investigator would compromise the safety of the patient or the quality of the data (e.g. tuberculosis, active serious infection, active systemic malignancy)
5. tuberculosis, active serious infection, active systemic malignancy,
6. or received a systemic medication for psoriasis within 3 months of study screening

CONCURRENT MEDICATIONS

All subjects should be maintained on the same medications throughout the entire study period, as medically feasible, with no introduction of new chronic therapies.

6.4 Allowed Medications and Treatments

Prohibited Medications and Treatments

The following medications are prohibited during the study and administration will be considered a protocol violation.

phototherapy, systemic medications for psoriasis (e.g. corticosteroids, other biologic medications, methotrexate, cyclosporine)

7 STUDY TREATMENTS

7.1 Method of Assigning Subjects to Treatment Groups

All patients in the trial are treated.

7.2 Blinding

None

7.3 Formulation of Test and Control Products

Standard manufacturer formulation

7.3.1 Formulation of Test Product

Standard manufacturer formulation

7.3.2 Formulation of Control Product

none

7.3.3 Packaging and Labeling

Standard manufacturer formulation

7.4 Supply of Study Drug at the Site

7.4.1 Dosage/Dosage Regimen

100 mg subcutaneous injection at 0, 4, and 16 weeks.

7.4.2 Dispensing

physician administered in clinic, From the investigational pharmacy at UCSF.

7.4.3 Administration Instructions

physician administered in clinic

7.5 Supply of Study Drug at the Site

physician administered in clinic

7.5.1 Storage

From the investigational pharmacy at UCSF.

7.6 Study Drug Accountability

By the investigational pharmacy at UCSF.

7.7 Measures of Treatment Compliance

physician administered in clinic

8 STUDY PROCEDURES AND GUIDELINES

A Schedule of Events representing the required testing procedures to be performed for the duration of the study is diagrammed in Appendix 1.

Prior to conducting any study-related activities, written informed consent and the Health Insurance Portability and Accountability Act (HIPAA) authorization must be signed and dated by the subject or subject's legal representative. If appropriate, assent must also be obtained prior to conducting any study-related activities.

8.1 Clinical Assessments

8.1.1 Concomitant Medications

All concomitant medication and concurrent therapies will be documented at Baseline/Screening visit. Dose, route, unit frequency of administration, and indication for administration and dates of medication will be captured.

8.1.2 Demographics

Demographic information (date of birth, gender, race) will be recorded at Screening.

8.1.3 Medical History

Relevant medical history, including history of current disease, other pertinent dermatologic history, review of systems, and information regarding underlying diseases will be recorded at Screening.

8.1.4 Physical Examination

A complete skin examination will be performed by either the investigator or a co-investigator who is a physician at Visit #1. Qualified staff (MD, NP, RN, and PA) may complete the abbreviated physical exam at all other visits. New abnormal physical exam findings must be documented and will be followed by a physician or other qualified staff at the next scheduled visit. Photographic documentation of pre and post-treatment psoriatic lesions will be obtained.

8.1.5 Vital Signs

In standard clinical (non-research) dermatology visits, vital signs are not typically monitored prior to/after skin biopsies unless the patient complains of feeling unwell.

8.1.6 Oximetry

No oximetry will be taken for this skin study.

8.1.7 Spirometry

No spirometry will be taken for this skin study.

8.1.8 Other Clinical Procedures

No other clinical procedures will be taken for this skin study.

8.1.9 Adverse Events

Information regarding occurrence of adverse events will be captured throughout the study. Duration (start and stop dates and times), severity/grade, outcome, treatment and relation to study drug will be recorded on the case report form (CRF).

8.2 Pharmacokinetic Measurements

No pharmacokinetic measurement will be taken for this skin study.

9 EVALUATIONS BY VISIT

9.1 Visit 1

1. Review the study with the subject (subject's legal representative) and obtain written informed consent and HIPAA authorization and assent, if appropriate.
2. Assign the subject a unique screening number.
3. Record demographics data.
4. Record medical history, including a history of rash, diagnosis date, and prior treatments.

5. Record concomitant medications.
6. Perform a complete skin examination.
7. Clean skin, anesthetize skin, take skin sample(s) (up to 2 6 mm punch biopsies), place suture.
8. Photograph of biopsied lesional skin and other psoriatic lesions
9. Part of the biopsied specimen will be sent for standard histopathology (if no previous histopathology from a similar representative lesion has been done)
10. Schedule subject for suture removal in 14 days.
11. Baseline routine bloodwork (CBC, quant gold, HIV, HB surface Ag, Anti-HB surface AB, anti-HB core AB, hepatitis C antibody, BUN/Creatinine, AST/ALT)

9.2 Visit 2 (2 weeks after Visit #1)

1. Remove suture.
2. Inspect biopsy site(s) to rule out infection.
3. Administration of tildrakizumab if normal baseline laboratory results, no interim medical issues, and/or histopathology consistent with psoriasis or atypical psoriasis (if no previous histopathology)

9.3 Visit 3 (4 weeks after Visit #2)

4. Interim medical history
5. Physical examination
6. Administration of tildrakizumab

9.4 Visit 4 (12 weeks after Visit #3)

7. Interim medical history
8. Physical examination
9. Administration of tildrakizumab

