SUBJECT SELECTION CRITERIA	
Inclusion Criteria: > 18 years of age, Patients with moderate-severe psoriasis or atypical psoriasis with either non-biologic treatment failure or > 5% body surface area affected.
 
Exclusion Criteria: tuberculosis, active serious infection, active systemic malignancy, or received a systemic medication for psoriasis within 3 months of study screening.

TEST PRODUCT, DOSE, AND ROUTE OF ADMINISTRATION	Tildrakizumab 100 mg subcutaneous injection
CONTROL PRODUCT, DOSE AND ROUTE OF ADMINISTRATION	n/a

DURATION OF SUBJECT PARTICIPATION AND DURATION OF STUDY	
The time commitment for the first visit will be approximately 1.5 hours to discuss the study, consent the patient, and perform the biopsy.
 
The second visit will last approximately 15 minutes
 
The third and fourth visits will last approximately 30 minutes.
 
With a total time committment of ~ 2 hrs 45 minutes

CONCOMMITANT MEDICATIONS	
Allowed:
 
Prohibited: other systemic medications for psoriasis

EFFICACY EVALUATIONS	
PRIMARY ENDPOINT	
 molecular gene expression profiling of skin cell populations.
SECONDARY ENDPOINTS	
 Psoriasis Area and Severity Index (PASI) score
OTHER EVALUATIONS	
SAFETY EVALUATIONS	
Re-evaluation of biopsy site at follow-up visit in 14 days for wound infection
 
In person medical visit for physical exam and history 4 weeks and 16 weeks after start of medication

PLANNED INTERIM ANALYSES	
When approximately 50% of patients have completed the study through Visit 4, an interim analysis for safety will be conducted by the investigator. Serious adverse events will be monitored by the committee on an ongoing basis throughout the study.

STATISTICS Primary Analysis Plan	
We will rely heavily on RNA-seq analysis, in some cases complemented with DNA sequencing and protein assessments. The RNAseq data will be normalized and compared in diseased vs normal skin and differential expression discerned at a significance level of 5% in a single test, in a two-group comparison, using a Negative Binomial mode. Numerous qualitative analyses will be performed as well.

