10.2.1 Serious Adverse Experience Reporting

Study sites will document all SAEs that occur (whether or not related to study drug) per [UCSF CHR Guidelines](#). The collection period for all SAEs will begin after informed consent is obtained and end after procedures for the final study visit have been completed.

In accordance with the standard operating procedures and policies of the local Institutional Review Board (IRB)/Independent Ethics Committee (IEC), the site investigator will report SAEs to the IRB/IEC.

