APPENDIX 1. EXAMPLE OF SCHEDULE OF STUDY VISITS

	VISIT 1 (Day 1)^a	VISIT 2 (Day 15)^a	VISIT 3 (DAY 43)*	VISIT 4 (DAY 127)*
Informed Consent	X			
Medical History	X	X	X	X
Skin Exam	X		X	X
Abbreviated Physical Exam		X		
Biopsy	X			
Suture removal and biopsy site check		X		
Treatment Administration		X	X	X
Baseline routine bloodwork	X			

^a ± 5 days

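### SAE collection closes at the visit where the third tildrakizumab injection is given, so 10 of 30 planned injections have no days of protocol SAE collection

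*Combined protocol and SAP*

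**What the plan says.** Section 7.4.1 sets the regimen: "100 mg subcutaneous injection at 0, 4, and 16 weeks". Section 9 places the doses at Visits 2, 3 and 4, and Appendix 1 dates these Days 15, 43 and 127. In section 9.4 the final Visit 4 item is "9. Administration of tildrakizumab".

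Section 10.2.1 asks for all SAEs, related to the drug or not. It opens the collection period at informed consent and says it will "end after procedures for the final study visit have been completed".

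Three other statements bear on the window:

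- Section 8.1.9, on adverse events generally: "Information regarding occurrence of adverse events will be captured throughout the study". It gives no end date.
- Synopsis, Safety Evaluations: "In person medical visit for physical exam and history 4 weeks and 16 weeks after start of medication". The later of these visits falls on the day of the third dose.
- Section 5.3: "Patients will have standard follow-up visits to assess efficacy and side effects of tildrakizumab", on the same footing as patients outside the trial. It gives no timing and does not mention SAE collection.

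**The concern.** The stop rule in 10.2.1 is explicit, so this is not a matter of detail left out. Applied as written, it closes SAE collection on a dosing day. A hospital admission the day after the third injection would meet the SAE definition in section 10.2 but fall outside the period in which the trial collects SAEs. Table 2 in section 10.1 grades relatedness partly by timing after administration, and for the third dose the protocol leaves no time in which to observe that.

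The third injection is a listed study procedure, supplied through the investigational pharmacy (section 7.4.2). One would expect the trial to collect serious events for some period after a dose that it gives. What is at stake is the completeness of the trial's safety record for one dose in three.

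**Working it through.** **Inputs.** Ten subjects (synopsis; section 13.6 agrees, with 10 samples). All are treated (section 7.1). Three doses each (7.4.1). Visit spacing of 2, 4 and 12 weeks (sections 9.2 to 9.4). End of SAE collection at completion of the final visit (10.2.1).

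**Step 1: reproduce the plan's visit days.** Starting from Day 1:

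- Visit 2: 1 + 14 = Day 15 (dose 1)
- Visit 3: 15 + 28 = Day 43 (dose 2)
- Visit 4: 43 + 84 = Day 127 (dose 3)

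These match Appendix 1. Measured from dose 1 they are weeks 0, 4 and 16, which match 7.4.1. Appendix 1 is titled an example, but it agrees with the body of the protocol.

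**Step 2: confirm that Visit 4 is the final visit.** Section 9 and Appendix 1 list nothing later, and the synopsis row on interim analyses treats Visit 4 as study completion. The synopsis visit times, taking 30 minutes each for Visits 3 and 4, sum to 90 + 15 + 30 + 30 = 165 minutes, or 2 h 45 min. The stated total is the same: "With a total time committment of ~ 2 hrs 45 minutes". There is no room for a fifth visit.

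**Step 3: days of SAE collection after each dose** (end of collection minus dose day).

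| Dose | Day given | Days to end of SAE collection |
|---|---|---|
| 1 | 15 | 127 − 15 = 112 |
| 2 | 43 | 127 − 43 = 84 |
| 3 | 127 | 127 − 127 = 0 |

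Visit windows would shift the first two figures by a few days. They cannot change the third, because dose and end of collection fall at the same visit.

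**Step 4: count.** 10 subjects × 3 doses = 30 planned injections, of which 10 are third doses: 10/30 = 33%. Replacement of withdrawals (section 12.4) could raise the total number of injections, but every third dose would still have 0 days.

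**Step 5: what could be missed (illustration only).** The documents give neither a post-dose window nor an SAE rate. Assume 28 days and 5 to 10 SAEs of any cause per 100 person-years. Uncollected time is 10 × 28 = 280 subject-days, or 0.77 person-years. Expected SAEs are 0.77 × 0.05 ≈ 0.038 to 0.77 × 0.10 ≈ 0.077. The chance of at least one is 1 − exp(−expected), or about 4% to 7%. On these assumptions, most likely no event would be missed.

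**The case against.** The best case for leaving the plan alone runs as follows. Tildrakizumab is approved for psoriasis and is given on its labelled schedule (section 1.2). Section 2.1 applies the same risk-benefit judgement as in ordinary clinic practice. Section 5.3 counts standard follow-up visits for side effects among the safety evaluations and sets no end to them. Each subject already has 112 days of SAE collection after first exposure, covering two identical doses. Ten unblinded, uncontrolled subjects support no safety inference that one late event would alter. Section 15.5 requires unanticipated problems to be reported, and section 15.2 requires the IRB to be told of new safety information. The institutional guidelines cited in 10.2.1 might themselves call for reporting after the study.

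Most of this stands, and it sets the size of the point. A reader might infer that patients are left unobserved after the third dose; section 5.3 does not support that. A reader might also infer a particular or delayed risk from the third dose, citing the background's remark on serious side effects. That remark concerns immunomodulatory drugs as a group and is made to justify predicting response. The documents give no evidence specific to dose 3.

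None of it extends the window. Section 5.3 provides care without SAE collection. Section 8.1.9 names no end beyond the study. The duties in sections 15.2 and 15.5 are narrower than collecting every SAE regardless of cause. The cited guidelines are not in the documents, and neither is some text after 10.2.1, where the contents list points to a medical monitoring section. Either could qualify the rule, though the stop rule itself is a complete sentence.

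**Conclusion.** The point holds as a gap in trial safety recording: 10 of 30 planned injections have 0 days of protocol SAE collection. The count assumes ten subjects who each receive all three doses. The zero rests only on Visit 4 being both the final visit and a dosing visit, on which the protocol is consistent.

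Severity is low. It would be wrong to read this as a threat to the trial's conclusions: the gene-expression analysis uses tissue taken before treatment, and assessment of response does not depend on when SAE collection closes. The probabilities in the working rest on assumed rates and cannot carry more weight than that. The reason to act is that the change is cheap.

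Confidence is medium, because the cited institutional guidelines and the text after 10.2.1 could not be read.

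**What to change.** 1. In section 10.2.1, end SAE collection at the later of the final study visit and 28 days after the subject's last tildrakizumab injection.
2. Give AE capture in section 8.1.9 the same end.
3. Add one telephone safety contact 28 days after the last injection to section 9, Appendix 1 and the synopsis participation statement. For a subject who receives all three doses this is about Day 155 (127 + 28). It should include subjects who stop the drug early, unless they withdraw consent.
4. State that the medication restrictions (Concurrent Medications and section 6.4) end at Visit 4, so that the telephone period does not constrain care.

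Twenty-eight days is a proposed minimum, not a figure from the plan. Twelve weeks, the plan's interval between doses 2 and 3, is an optional longer choice. It would move the call to Day 211 (127 + 84) and elapsed participation to 126 + 84 = 210 days (+67%).

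**Cost with 28 days.** About one call per treated subject (10, plus any replacements), one CRF page and a line in the consent form. No clinic visit, blood test or biopsy is added. Elapsed participation rises from 126 to 126 + 28 = 154 days (28/126 = 22%). The safety data lock moves 28 days later, but the RNA and Visit 4 response analyses need not wait. Some subjects may not be reached, and treatments started after Visit 4 may make causality harder to judge for late events.

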10 ADVERSE EXPERIENCE REPORTING AND DOCUMENTATION

10.1 Adverse Events

An adverse event (AE) is any untoward medical occurrence in a clinical investigation of a pharmaceutical product and that does not necessarily have a causal relationship with the treatment.

AE Severity

The National Cancer Institute's Common Terminology Criteria for Adverse Events (CTCAE) Version 3.0 should be used to assess and grade AE severity, including laboratory abnormalities judged to be clinically significant. The modified criteria can be

found in the study manual. If the experience is not covered in the modified criteria, the guidelines shown in Table 1 below should be used to grade severity. It should be pointed out that the term “severe” is a measure of intensity and that a severe AE is not necessarily serious.

Table 1. AE Severity Grading

Severity (Toxicity Grade)	Description
Mild (1)	Transient or mild discomfort; no limitation in activity; no medical intervention or therapy required. The subject may be aware of the sign or symptom but tolerates it reasonably well.
Moderate (2)	Mild to moderate limitation in activity, no or minimal medical intervention/therapy required.
Severe (3)	Marked limitation in activity, medical intervention/therapy required, hospitalizations possible.
Life-threatening (4)	The subject is at risk of death due to the adverse experience as it occurred. This does not refer to an experience that hypothetically might have caused death if it were more severe.

AE Relationship to Study Drug

The relationship of an AE to the study drug should be assessed using the following the guidelines in Table 2.

Table 2. AE Relationship to Study Drug

Relationship to Drug	Comment
Definitely	Previously known toxicity of agent; or an event that follows a reasonable temporal sequence from administration of the drug; that follows a known or expected response pattern to the suspected drug; that is confirmed by stopping or reducing the dosage of the drug; and that is not explained by any other reasonable hypothesis.
Probably	An event that follows a reasonable temporal sequence from administration of the drug; that follows a known or expected response pattern to the suspected drug; that is confirmed by stopping or reducing the dosage of the drug; and that is unlikely to be explained by the known characteristics of the subject’s clinical state or by other interventions.
Possibly	An event that follows a reasonable temporal sequence from administration of the drug; that follows a known or expected response pattern to that suspected drug; but that could readily have been produced by a number of other factors.
Unrelated	An event that can be determined with certainty to have no relationship to the study drug.

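### As punctuated, Table 2 lets known toxicity alone earn the grade *Definitely*, with no condition on timing or other causes, so a coincidental event of a known type can receive the top causality grade

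*Combined protocol and SAP*

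**What the plan says.** Section 10.1, Table 2, offers four causality grades as guidelines. The *Definitely* row begins "Previously known toxicity of agent; or an event that follows a reasonable temporal sequence from administration of the drug". It continues with a known response pattern, a dechallenge condition ("that is confirmed by stopping or reducing the dosage of the drug") and an alternative-cause condition ("and that is not explained by any other reasonable hypothesis").

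*Probably* repeats the timing, pattern and dechallenge conditions and adds that another explanation is unlikely. *Possibly* requires timing and pattern, "but that could readily have been produced by a number of other factors". *Unrelated* is "An event that can be determined with certainty to have no relationship to the study drug". Nothing states which grade prevails when two fit.

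On collection, section 8.1.9 says "Information regarding occurrence of adverse events will be captured throughout the study" and has the relationship to study drug entered on the CRF, together with start and stop dates and times. For serious events, section 10.2.1 says "The collection period for all SAEs will begin after informed consent is obtained". The first injection comes at Visit 2, two weeks after Visit 1; section 9.2 lists "Administration of tildrakizumab if normal baseline laboratory results" among its conditions.

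**The concern.** A causality scale should become harder to satisfy as the grade rises. Here the top grade has an entry route that asks only what type of event occurred. Timing, course after stopping the drug and competing causes play no part in that route, although timing is required for both grades below it.

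This matters more than usual because the study has no comparator (sections 7.1 and 7.3.2), so there is no control rate against which to judge background illness. Competing causes are also built in. Every subject is biopsied, and section 2.1 lists bleeding, pain, infection and allergic reaction to the anesthetic among the biopsy risks. The documents do not list the known toxicities of tildrakizumab, so any overlap with those biopsy risks is an assumption.

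At stake is whether the recorded relationship means anything for event types already associated with the drug. Two assessors who both follow the table could put the same event at opposite ends of the related grades.

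**Working it through.** The plan states no figure on this point, so the check is mainly a reading of the table.

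**Step 1. Logical form.** In the *Definitely* row, each clause after the semicolon begins with *that* and describes the event introduced there. The natural reading is:

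known toxicity OR (timing AND pattern AND dechallenge AND no other explanation)

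The first term is enough to make the whole expression true.

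**Step 2. Conditions side by side.**

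| Route | Timing | Known type or pattern | Dechallenge | Other causes |
|---|---|---|---|---|
| *Definitely*, first limb | not stated | required | not stated | not stated |
| *Definitely*, second limb | required | required | required | none reasonable |
| *Probably* | required | required | required | unlikely |
| *Possibly* | required | required | not required | readily available |
| *Unrelated* | – | – | – | certain absence of relationship |

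**Step 3. Events of a known type, and the grades that fit.**

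- (a) After dosing, well timed, other causes readily available, no dechallenge: *Definitely* (first limb) and *Possibly*.
- (b) Onset before the first injection: *Unrelated*, and also *Definitely* if the first limb is read as event type alone.
- (c) After dosing, well timed, no other cause, no dechallenge: *Definitely* (first limb) only.
- (d) After dosing, implausible timing, not certain to be unrelated: *Definitely* (first limb) only.

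Cases (a) and (b) show the overlap. Case (c) shows that the first limb also does necessary work. With single injections at 0, 4 and 16 weeks (section 7.4.1), dechallenge will often be unavailable, and without the first limb such a reaction would fit no grade.

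**Step 4. Is there a pre-dose window?** Appendix 1 puts Visit 1 at Day 1, Visit 2 at Day 15 and Visit 4 at Day 127. Pre-dose time is 15 − 1 = 14 days out of 127 − 1 = 126, and 14/126 = 11%. If only Visit 2 moves within its ±5 days, the window is 9 to 19 days. The window exists, but 11% is a share of days, not of events.

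**Step 5. Size.** With 10 subjects, one affected subject is 1/10 = 10 percentage points of any per-subject proportion. How often this would happen depends on two quantities that the documents do not give: p, the chance that a subject has a coincidental event of a known type, and m, the chance that an assessor grades it through the first limb. The chance of at least one such grading is 1 − (1 − p·m)^10. Assuming p = 5%, 10% or 20%, m = 1 gives 40%, 65% or 89%, and m = 0 gives 0% throughout. That range is too wide to serve as an estimate.

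**The case against.** The strongest reply is that the table is guidance applied by a clinician and nothing forces the first limb to be used. A coincidental event after dosing already has a home in *Possibly*. An event before any injection can be called unrelated with certainty, a toxicity of an agent presupposes exposure to it, and the recorded start date makes a pre-dose onset visible. A reader could also apply the later conditions to both limbs.

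Much of this stands. A reader might infer that coincidental and pre-dose events will be recorded as certain drug reactions. The documents do not support that: they permit such a grading but do not require it, and the pre-dose case is the weakest example. Nor do they support treating the m = 1 figures as error rates, since those assume that every assessor always uses the first limb.

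The reply is also right about consequences. Serious events are documented whatever their cause (section 10.2.1) and reported to the ethics board on the same basis (section 15.2). Section 13 plans no analysis by causality grade. The synopsis mentions an interim look at safety, but does not say that it uses the grade.

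What does not stand is reliance on assessors to read past the wording. If the right grade is reached only by ignoring the literal text, the text needs correcting.

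**Conclusion.** The point holds in limited form. As punctuated, known toxicity alone satisfies *Definitely*. For known event types the top grade is therefore easier to reach than the two below it, and it overlaps with *Possibly* and, before the first dose, with *Unrelated*, with no precedence rule. A coincidental event of a known type can be recorded as certainly drug-related.

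The consequence is confined to the CRF relationship field and any safety summary later built on it. Capture of serious events and the gene-expression endpoint are untouched. The frequency of misgrading cannot be derived from the documents. The conclusion rests on the natural grammatical reading of the row, not on any event rate.

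**What to change.** Keep the known-toxicity limb in the *Definitely* row and qualify it with two conditions that the second limb already carries: plausible timing after administration, and no other reasonable explanation. Leave dechallenge out of this limb.

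Under that wording case (a) goes to *Possibly*, case (b) to *Unrelated*, and case (c) stays in *Definitely*. Deleting the limb would be the wrong repair: *Definitely* and *Probably* would then both require dechallenge and *Possibly* would require a ready alternative cause, so case (c) would fit nothing.

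Optionally, add a line that *Unrelated* takes precedence when onset is before the first injection. Case (d) would no longer meet *Definitely* and would fit no grade as the table stands, so the sponsor should also state how such an event is to be graded.

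The cost is one edit to Table 2 and the matching CRF instructions, with no added visits or procedures. The downside is small: some known-type events would move from *Definitely* to *Possibly*, and each would need a short judgement on timing and other causes.
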